## 5 BIOSPECIMEN COLLECTION

### 5.1 CORRELATIVE STUDIES FOR RESEARCH/PHARMACOKINETIC STUDIES

The time of enzalutamide dose administration is  $t = 0$  for purposes of pharmacokinetic sample collection times. Due to the long  $t_{1/2}$  of enzalutamide, *N*-desmethyl enzalutamide, and the carboxylic acid metabolite in healthy subjects (approximately 6, 8, and 10 days, respectively [7]), pharmacokinetic samples will be collected over 42 days.

With each 160 mg dose of enzalutamide, pharmacokinetic blood samples will be collected in 6-mL tubes with dipotassium ethylenediaminetetraacetic acid (K2 EDTA) as the anticoagulant. Venous blood samples for plasma will be collected at the following times: pre-dose (0 hr) and post-dose at 30 minutes; and at 1, 2, 4, and 8 hours (Day 1), 24h (Day 2), 48h (Day 3), 168h (Day 8), and Day 42 post-dose.

Validated bioanalytical methods based on ultra high-performance liquid chromatography with tandem mass spectrometry (uHPLC-MS/MS) [10] will be developed by the Clinical Pharmacology Program and used to analyze plasma samples for concentrations of enzalutamide and the two major human metabolites (e.g. *N*-desmethyl enzalutamide and carboxylic acid enzalutamide).

Non-compartmental PK analysis of enzalutamide in plasma will be performed using WinNonlin 5.0 (Pharsight, Inc., Mountain View, CA). PK parameters derived from plasma concentration-time data may include  $C_{max}$ ,  $T_{max}$ , AUC, Cl, Cl/F, Vd, and  $t_{1/2}$ .

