#### **1.2.2 Pharmacokinetic Studies**

Multiple clinical pharmacokinetic studies of enzalutamide have been conducted [7]. Enzalutamide has a half-life of 5.8 days, achieves steady state by day 28, accumulates 8.3-fold with once-daily dosing, shows approximate dose proportionality from 30–360 mg/day, and has <30 % intersubject variability. It is primarily eliminated by hepatic metabolism, while renal excretion is an insignificant elimination pathway for enzalutamide and its active metabolite, N – desmethyl enzalutamide. Exposure to enzalutamide active moieties is not affected by food or baseline mild or moderate hepatic impairment. Enzalutamide has predictable pharmacokinetics, with low intersubject variability. Similar efficacy was observed in patients across the concentration/exposure range associated with a fixed oral dose of enzalutamide 160 mg/day.

*Abbreviated Title: Enzalutamide Formulation PK*  
*Version Date: 03.11.2020*

Study NCT01911715 was a phase I, open-label, one-period, single-dose mass balance and biotransformation study in six healthy male subjects [7]. After a single oral dose of enzalutamide 160 mg (4 x 40 mg capsules), at least 84.2% of the drug was absorbed. The average  $C_{max}$ ,  $t_{max}$ ,  $AUC_{inf}$ , and  $t_{1/2}$  of enzalutamide were 4.5 ug/mL, 1.8 h, 237 ug\*h/mL, and 2.9 days, respectively.

A phase I, open-label, randomized, single-dose, parallel design, food-effect study was performed in 60 healthy men (n=30 in fasted and fed arms) to determine the effect of a high-fat meal on the pharmacokinetics of enzalutamide [7]. The average  $C_{max}$  and  $T_{max}$  for the fasted and fed arms were 5.3 and 3.7 ug/mL and 1 and 2h post-dose, respectively. The average  $AUC_{inf}$  for the fasted and fed arms were 292 and 285 ug\*h/mL, respectively. In all, the data suggest that consumption of a high-fat meal slightly slows the rate of absorption but does not lower exposure of enzalutamide.

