## **8 STATISTICAL CONSIDERATIONS**

### **8.1 STATISTICAL HYPOTHESES**

#### **Primary efficacy endpoints:**

To evaluate the bioequivalence of two oral formulations of enzalutamide following a single 160 mg dose in male subjects with prostate cancer.

The primary measure of efficacy will be AUC for the first period of administration obtained during blood draws during visits on day 1, 3, 8, and 42 evaluations, and then AUC at a second set of visits at least 42 days after the first administration, for evaluations on days 1, 3, 8 and 42 relative to the second administration, for the second period evaluations.

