#### 8.4.2 Analysis of the Primary Efficacy Endpoints

The average of the AUC values at the 4 determinations associated with each of the two drug administrations will be determined and the difference assessed for statistical significance at the 0.05 level using the non-parametric procedures identified in the Koch 1972 paper.

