#### 8.4.9 Exploratory Analyses

There are no exploratory objectives so no exploratory analyses will be undertaken.

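### The bioequivalence conclusion would rest on AUC alone: no comparison of peak exposure (Cmax) is planned, although the samples for it are already drawn

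*Combined protocol and SAP*

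**What the plan says.** Section 1.1.1 makes bioequivalence of the two formulations the primary objective. The statistical sections then deal with AUC only:

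- **Endpoint (8.1):** "The primary measure of efficacy will be AUC for the first period of administration", with a second AUC for the second period.
- **Margins and power (8.2):** the equivalence region for liquid minus capsule is −40 to 0 ug*h/mL of AUC, with an expected difference of −20, a standard deviation of differences of 20, 12 evaluable men and 5% per test.
- **Analysis (8.4.1 and 8.4.2):** "The average of the AUC values at the 4 determinations associated with each of the two drug administrations will be determined", and the difference is tested with the Koch non-parametric procedure.
- **Secondary analysis (8.4.3):** nausea and vomiting.
- **Exploratory analysis (8.4.9):** "There are no exploratory objectives so no exploratory analyses will be undertaken".

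As an outcome of this trial, Cmax appears only in section 5.1, in the list introduced by "PK parameters derived from plasma concentration-time data may include". The same section schedules samples before the dose, at 0.5, 1, 2, 4, 8, 24, 48 and 168 hours, and on Day 42.

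Section 1.2.2 describes the cited food study. Mean Cmax and Tmax "for the fasted and fed arms were 5.3 and 3.7 ug/mL and 1 and 2h post-dose, respectively", mean AUCinf in ug*h/mL "for the fasted and fed arms were 292 and 285", and the protocol concludes that a high-fat meal "slightly slows the rate of absorption but does not lower exposure of enzalutamide".

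**The concern.** Bioequivalence is a statement about rate as well as extent of absorption, and AUC measures extent. The protocol draws the same distinction when it reads the food study. The test product is the capsule's own liquid taken without the shell (sections 1.2.4 and 10.1.3.2), so rate is a natural property to check, alongside any loss of dose in extraction or in the syringe.

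Followed as written, the trial could report two formulations as bioequivalent while their peaks had never been compared. A reader would take the claim to cover peak exposure; the analysis would support only extent.

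**Working it through.** **1. The plan's own figure.** For two one-sided t-tests in a 2×2 crossover, SE = 20/√12 = 5.77 with 10 degrees of freedom. With margins −40 and 0 and a true difference of −20, exact power is 78.4% at N = 10 and 88.4% at N = 12. Twelve is therefore the smallest balanced number reaching the stated 80%. All of this power is for AUC.

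**2. How much of AUC the peak can carry.** Area over the first 8 hours cannot exceed Cmax × 8. With the means in section 1.2.2:

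| Study | Cmax × 8 (ug*h/mL) | AUCinf (ug*h/mL) | Largest share |
|---|---|---|---|
| Food study, fasted | 5.3 × 8 = 42.4 | 292 | 14.5% |
| Mass-balance study | 4.5 × 8 = 36.0 | 237 | 15.2% |

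If every concentration in the first 8 hours were 30% lower and all later ones unchanged, AUC would fall by at most 0.30 × 42.4 = 12.7 ug*h/mL, or 4.4% of 292. As a true difference, that lies well inside −40 to 0.

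**3. Can the two measures separate?** In the food study, fed over fasted:

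- Cmax: 3.7/5.3 = 0.70, a fall of 30%.
- AUCinf: 285/292 = 0.98, a fall of 2.4%.

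**4. Can Cmax be derived from the planned samples?** The cited mean Tmax values are 1, 1.8 and 2 hours. The draws at 0.5, 1, 2, 4 and 8 hours bracket them.

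**5. What 12 men would show about Cmax.** The documents give neither a within-subject CV nor limits for Cmax, so both are assumed here. On the log scale the half-width of the 90% interval is 1.812 × √2 × √ln(1 + CV²) / √12. The last three columns give the chance that the interval lies within 0.80–1.25.

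| Assumed CV | 90% interval centred on 1 | True ratio 1 | True ratio 0.95 | True ratio 0.70 |
|---|---|---|---|---|
| 15% | 0.90–1.12 | 92% | 83% | under 0.1% |
| 20% | 0.86–1.16 | 64% | 57% | 0.1% |
| 25% | 0.83–1.20 | 35% | 31% | 0.2% |

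A 30% fall in Cmax would almost never be declared equivalent, but a true match might well go unproven.

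**The case against.** **The food study is indirect.** It compared fed with fasted men in parallel groups, whereas both periods here are fasted. A reader might infer that the liquid will have a lower Cmax, or that rate is what removing the shell is most likely to change. The documents support neither. The expectation stated in section 8.2 is a loss of extent, about 10% of AUC. Sections 3.2 and 10.1.4 likewise deal with residual drug in the syringe and a 3.04% fall in concentration over 24 hours. The food study stands only as evidence that Cmax and AUC can part company.

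**The wording in section 5.1 is weak evidence.** The same optional list contains AUC, the primary endpoint, so the wording does not by itself demote Cmax. That is correct. The point rests on section 8 giving Cmax no analysis.

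**The consequence is limited.** The trial is called a pilot (sections 1.2.4 and 3.1), and section 10 says it is not meant to support a significant labeling change. Section 1.2.2 reports 8.3-fold accumulation and similar efficacy across the exposure range. If single-dose AUCinf approximates AUC over a dosing interval at steady state, the average concentration is about 292/24 = 12.2 ug/mL. The food study's peak difference of 5.3 − 3.7 = 1.6 ug/mL is 13% of that. This lowers the stakes but does not justify an unqualified bioequivalence claim under an objective worded that way.

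**Twelve men may be too few for Cmax.** This stands. A reader might infer from the interval widths that the data will settle the matter; the probabilities in the table show that they may not.

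**Conclusion.** The gap is real and concerns endpoint and analysis, not sampling. As planned, a bioequivalence conclusion would be one about extent of absorption only, for a drug whose first 8 hours carry at most about 15% of AUC on the cited means.

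A reader might also infer that the plan's AUC rule would have passed the food-study pair despite its 30% difference in Cmax. The plan's margins do not support that. The pair differs by 285 − 292 = −7; with SE 5.77 the 90% interval centred there is −7 ± 10.5, or −17.5 to +3.5, which crosses the upper margin of 0. The exact chance of passing with 12 men is about 30%. The 88% power applies to a true difference of −20.

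The conclusion rests on the texts of sections 1.1.1, 5.1 and 8 and on the means in section 1.2.2. The Cmax probabilities rest on assumed CVs and assumed limits. It is worth correcting because the change is cheap and alters what the trial may claim; it does not undermine the AUC analysis.

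**What to change.** 1. **Section 5.1:** state that Cmax, Tmax and AUC *will* be derived for each administration.
2. **Sections 8.1 and 8.4:** add Cmax as a key secondary endpoint. Report the within-patient liquid/capsule ratio on the log scale with a 90% confidence interval, from a crossover analysis with sequence and period or from a Koch-type rank procedure with a matching interval. Choose one in advance. The plan contains no parametric crossover model for Cmax to borrow, so the method must be written out. Report Tmax descriptively.
3. **Limits:** prespecify those against which the Cmax interval is read. The range 0.80–1.25 is offered as an assumption.
4. **Wording of the conclusion:** if the Cmax interval does not support equivalence or is inconclusive, describe a positive AUC result as equivalence in extent of absorption (AUC), not as bioequivalence.

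The primary AUC analysis is not changed by this item.

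**Cost.** No added patients, visits or blood draws; a short addition to the analysis text. The unqualified claim becomes harder to reach. In simulation under the plan's AUC assumptions, with a true Cmax ratio of 0.95 and a correlation of 0 to 0.5 between the measures, the chance of meeting both criteria is about 73–75%, 50–52% and 28–29% at assumed CVs of 15%, 20% and 25%, against 88% for AUC alone. The fallback wording keeps the AUC result reportable in every case.

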### 5.3 SAMPLE STORAGE, TRACKING AND DISPOSITION

Samples will be ordered in CRIS and tracked through a Clinical Trial Data Management system. Should a CRIS screen not be available, the CRIS downtime procedures will be followed. Samples will not be sent outside NIH without appropriate approvals and/or agreements, if required.

Any transfer of materials to other NIH or non-NIH investigators will occur following NIH Intramural Research Program guidelines. If the subject withdraws consent the participants data will be excluded from future distributions, but data that have already been distributed for approved research use will not be able to be retrieved.

*Abbreviated Title: Enzalutamide Formulation PK*  
*Version Date: 03.11.2020*

Upon arrival in the Clinical Pharmacology Program (CPP), blood samples will be centrifuged and the plasma transferred into cryovials for storage at -80° C until the time of analysis.

All PK samples will be barcoded, with data entered and stored in the LABrador (aka LabSamples) utilized by the CPP. This is a secure program, with access to LABrador System limited to defined CPP personnel, who are issued individual user accounts. The program creates a unique barcode ID for every sample and sample box, which cannot be traced back to patients with LABrador access. The data recorded for each sample includes the patient ID, name, trial name/protocol number, time drawn, cycle time point, dose, material type, as well as box and freezer locations. Patient demographics associated with the clinical center patient number are provided in the system. For each sample, there are notes associated with the processing method (e.g. delay in sample processing, storage conditions on the ward, etc.).

Barcoded samples are stored in barcoded boxes in locked freezers at either -20 C or -80 C according to stability requirements. These freezers are located onsite in the CPP and offsite at NCI Frederick Central Repository Services in Frederick, MD. Samples will be stored until requested by a researcher named on the protocol.

All requests are monitored and tracked in LABrador. All researchers are required to sign a form stating that the samples are only to be used for research purposes associated with this trial (as per IRB approved protocol) and that any unused samples must be returned to the CPP.

Following completion of this study, samples will remain in storage as detailed above. Access to these samples will only be granted following IRB approval of an additional protocol, granting the rights to use the material.

If, at any time, a patient withdraws from the study and does not wish for their existing samples to be utilized, the individual must provide a written request. Following receipt of this request, the samples will be destroyed (or returned to the patient, if so requested), and reported as such to the IRB. The PI will record any loss or unanticipated destruction of samples as a deviation.

Reporting will be per the requirements of Section 7.2.

Sample barcodes are linked to patient demographics and limited clinical information. This information will only be provided to investigators listed on this protocol, via registered use of the LABrador. It is critical that the sample remains linked to patient information such as race, age, dates of diagnosis and death, and histological information about the tumor, in order to correlate pharmacokinetic data with these variables.

## **6 DATA COLLECTION AND EVALUATION**

### **6.1 DATA COLLECTION**

C3D and LABrador will be used for data collection purposes. The PI will be responsible for overseeing entry of data into an in-house password protected electronic system and ensuring data accuracy, consistency and timeliness. The principal investigator, associate investigators/research nurses and/or a contracted data manager will assist with the data management efforts. All data obtained during the conduct of the protocol will be kept in secure network drives or in approved alternative sites that comply with NIH security standards. Primary and final analyzed data will have identifiers so that research data can be attributed to an individual human subject participant.

*Abbreviated Title: Enzalutamide Formulation PK*  
*Version Date: 03.11.2020*

All adverse events, including clinically significant abnormal findings on laboratory evaluations, regardless of severity, will be followed until return to baseline or stabilization of event.

An abnormal laboratory value will be recorded in the database as an AE **only** if the laboratory abnormality is characterized by any of the following:

- Results in discontinuation from the study
- Is associated with clinical signs or symptoms
- Requires treatment or any other therapeutic intervention
- Is associated with death or another serious adverse event, including hospitalization.
- Is judged by the Investigator to be of significant clinical impact
- If any abnormal laboratory result is considered clinically significant, the investigator will provide details about the action taken with respect to the test drug and about the patient's outcome.

**End of study procedures:** Data will be stored according to HHS, FDA regulations, and NIH Intramural Records Retention Schedule as applicable.

**Loss or destruction of data:** Should we become aware that a major breach in our plan to protect subject confidentiality and trial data has occurred, this will be reported expeditiously per requirements in Section [7.2.1](#).

## **6.2 DATA SHARING PLANS**

### **6.2.1 Human Data Sharing Plan**

#### **What data will be shared?**

I will share human data generated in this research for future research as follows:

- Coded, linked data in an NIH-funded or approved public repository.
- Coded, linked data in BTRIS (automatic for activities in the Clinical Center)

#### **How and where will the data be shared?**

Data will be shared through:

- An NIH-funded or approved public repository. Insert name or names: ClinicalTrials.gov.
- BTRIS (automatic for activities in the Clinical Center)
- Approved outside collaborators under appropriate individual agreements.
- Publication and/or public presentations.

#### **When will the data be shared?**

- Before publication.
- At the time of publication or shortly thereafter.

*Abbreviated Title: Enzalutamide Formulation PK*  
*Version Date: 03.11.2020*

### **6.3 TOXICITY CRITERIA**

The following adverse event management guidelines are intended to ensure the safety of each patient while on the study. The descriptions and grading scales found in the revised NCI Common Terminology Criteria for Adverse Events (CTCAE) version 5.0 will be utilized for AE reporting. All appropriate treatment areas should have access to a copy of the CTCAE version 5.0. A copy of the CTCAE version 5.0 can be downloaded from the CTEP web site ([http://ctep.cancer.gov/protocolDevelopment/electronic\\_applications/ctc.htm](http://ctep.cancer.gov/protocolDevelopment/electronic_applications/ctc.htm)).

## **7 NIH REPORTING REQUIREMENTS / DATA AND SAFETY MONITORING PLAN**

### **7.1 DEFINITIONS**

Please refer to definitions provided in Policy 801: Reporting Research Events found [here](#).

### **7.2 OHSRP OFFICE OF COMPLIANCE AND TRAINING / IRB REPORTING**

#### **7.2.1 Expedited Reporting**

Please refer to the reporting requirements in Policy 801: Reporting Research Events and Policy 802 Non-Compliance Human Subjects Research found [here](#).

#### **7.2.2 IRB Requirements for PI Reporting at Continuing Review**

Please refer to the reporting requirements in Policy 801: Reporting Research Events found [here](#).

### **7.3 FDA REQUIREMENTS**

The person conducting the study must retain reserve samples of any test article and reference standard used in the study and release the reserve samples to FDA upon request, in accordance with, and for the period specified in, 320.38 (at least 5 years following the date of completion of the bioavailability study in which the sample from which the reserve sample was obtained was used).

The PI or AI must notify FDA and all participating investigators of any serious adverse event, observed during the conduct of the study as soon as possible but in no case later than 15 calendar days after becoming aware of its occurrence. Each report must be submitted on FDA Form 3500A or in an electronic format that FDA can process, review, and archive. Each report must bear prominent identification of its contents, i.e., "bioavailability/bioequivalence safety report." The person conducting the study must also notify FDA of any fatal or life-threatening adverse event from the study as soon as possible but in no case later than 7 calendar days after becoming aware of its occurrence. Each notification under this paragraph must be submitted to the Director, Office of Generic Drugs in the Center for Drug Evaluation and Research at FDA. Relevant followup information to a bioavailability/bioequivalence safety report must be submitted as soon as the information is available and must be identified as such, i.e., "Followup bioavailability/bioequivalence safety report." Upon request from FDA, the person conducting the study must submit to FDA any additional data or information that the agency deems necessary, as soon as possible, but in no case later than 15 calendar days after receiving the request.

*Abbreviated Title: Enzalutamide Formulation PK*  
*Version Date: 03.11.2020*

## **7.4 NCI CLINICAL DIRECTOR RERPORTING**

Problems expeditiously reported to the OHSRP in iRIS will also be reported to the NCI Clinical Director. A separate submission is not necessary as reports in iRIS will be available to the Clinical Director.

In addition to those reports, all deaths that occur within 30 days after receiving a research intervention should be reported via email to the Clinical Director unless they are due to progressive disease.

To report these deaths, please send an email describing the circumstances of the death to [name] at [contact] within one business day of learning of the death.

## **7.5 NIH REQUIRED DATA AND SAFETY MONITORING PLAN**

### **7.5.1 Principal Investigator/Research Team**

The clinical research team will meet on a regular basis (at least weekly) when patients are being actively treated on the trial to discuss each patient. Decisions about dose level enrollment and dose escalation if applicable will be made based on the toxicity data from prior patients.

All data will be collected in a timely manner and reviewed by the principal investigator or a lead associate investigator. Events meeting requirements for expedited reporting as described in Section 7.2.1 will be submitted within the appropriate timelines.

The principal investigator will review adverse event and response data on each patient to ensure safety and data accuracy. The principal investigator will personally conduct or supervise the investigation and provide appropriate delegation of responsibilities to other members of the research staff.

## **8 STATISTICAL CONSIDERATIONS**

### **8.1 STATISTICAL HYPOTHESES**

#### **Primary efficacy endpoints:**

To evaluate the bioequivalence of two oral formulations of enzalutamide following a single 160 mg dose in male subjects with prostate cancer.

The primary measure of efficacy will be AUC for the first period of administration obtained during blood draws during visits on day 1, 3, 8, and 42 evaluations, and then AUC at a second set of visits at least 42 days after the first administration, for evaluations on days 1, 3, 8 and 42 relative to the second administration, for the second period evaluations.

